### **3.3. Correlation between PPFEV1 and CFQ-R RSS**

The relationship between PPFEV1 and CFQ-R RSS will be assessed with Pearson correlations and scatterplots with regression lines for:

- Baseline: Actual values, overall
- Day 33: Actual values and changes from baseline, by treatment group
- Day 26 pre-dose for PPFEV1 and Day 33 for CFQ-R RSS: Actual values and changes from baseline, by treatment group

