## **4. STATISTICAL METHODS**

### **4.1. Sample Size Justification**

This is a Phase 1 safety study designed to evaluate the safety, tolerability and PK of QR-010. The sample size is not based on power calculations. It is chosen based on clinical experience and considered to be adequate to fulfill the objectives of the study.

Approximately 64 subjects will be enrolled in the study, with 8 subjects per cohort (6 QR-010 and 2 placebo), 32 each in the SAD and MAD portions of the study. The exact number of subjects enrolled is dependent on whether any dose levels are to be expanded due to the occurrence of AEs of interest.

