#### 4.8.2.9. CFQ-R (Cystic Fibrosis Questionnaire – Revised)

The CFQ-R subject health-related quality of life questionnaire will be administered using the self-administered format (Adolescent and Adult version in the protocol Appendix 3), according

to the study schedule for MAD cohorts only. The CFQ-R is administered prior to any other test or procedure on each of the required study days (Baseline, Day 15, Day 33 and Day 54).

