#### Cystic Fibrosis Questionnaire- Revised Respiratory Symptoms Score (CFQ-R RSS)

The CFQ-R RSS is calculated based on mean score of Questions 40 to 46 excluding question 43 as below if  $\leq 3$  item scores are missing:

Assuming a coding of 1 to 4 with categories such as

1=A great deal / Always

2=Somewhat / Often

3=A little / Sometimes

4=Not at all / Never,

$$\text{CFQ-R RSS} = \text{mean} [(\text{resp40}, \text{resp41}, \text{resp42}, \text{resp44}, \text{resp45}, \text{resp46})-1]/3*100;$$

The score will be missing if more than three of the six scores are missing.

Descriptive summary overtime will be provided for the values and change from baseline at each time point following the time windows, by treatment group.

A mixed model analysis with repeated time measures on the change from baseline of CFQ-R RSS as outcome variable, including treatment, baseline CFQ-R RSS value, time and interaction between time and treatment as covariates will be performed. By default, an unstructured covariance matrix will be used, unless convergence issue occurs, in which case other covariance matrix will be explored. Adjusted means and corresponding confidence interval will be presented. The following time points will be included in the repeated measures analysis: Baseline, Day 15, Day 33 and Day 54. Differences versus placebo will be estimated at Day 33 and Day 54.

A dose-response analysis using MCPMOD methodology will be performed with change from baseline of CFQ-R RSS at Day 33 as dependent variable, the treatment (0, 6.25, 12.5, 25, 50 mg) and CFQ-R RSS at baseline as factors. Thresholds of +4, +5, +8 and +10 will be tested as sizes of interest of treatment effect.

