### 2.2. Subgroups Definitions

To explore the impact of the baseline status:

Subgroups of subjects with PPFEV1  $< 90$  and  $\geq 90\%$  at baseline will be considered for PPFEV1 and CFQ-R RSS endpoints analyses.

Subgroups of subjects with CFQ-R RSS  $< 75$  and  $\geq 75$  at baseline will be considered for CFQ-R RSS endpoints analyses.

The following subgroups of CFQ-R RSS at baseline by range of 10 points will also be considered for CFQ-R RSS analyses: ..., [50;60[, [60;70[, [70;80[, [80;90[, [90;100].

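### After baseline, the addendum correlates ppFEV1 with CFQ-R RSS only within arms of about 6 to 8 subjects, too few to tell strong from absent correlation in most cases; an arm-adjusted correlation over all MAD subjects should be added.

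*SAP*

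**What the plan says.** Section 3.3 of the SAP addendum states the method: "The relationship between PPFEV1 and CFQ-R RSS will be assessed with Pearson correlations and scatterplots with regression lines for" three situations.

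- Baseline: "Baseline: Actual values, overall".
- Same-day pairing: "Day 33: Actual values and changes from baseline, by treatment group".
- Lagged pairing: "Day 26 pre-dose for PPFEV1 and Day 33 for CFQ-R RSS: Actual values and changes from baseline, by treatment group".

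Only the baseline correlation uses all subjects together. No overall or arm-adjusted correlation, and no confidence interval, is planned after baseline. The section names no analysis population.

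The arm sizes follow from the main SAP. CFQ-R is administered according "to the study schedule for MAD cohorts only" (section 4.8.2.9), so only MAD subjects contribute. Section 4.1 plans the study "with 8 subjects per cohort (6 QR-010 and 2 placebo), 32 each in the SAD and MAD portions of the study". Placebo subjects from the four MAD cohorts form a single group: the CFQ-R RSS dose-response model uses "the treatment (0, 6.25, 12.5, 25, 50 mg) and CFQ-R RSS at baseline as factors", and the MAD table header (Table 4) has one placebo column.

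**The concern.** A correlation coefficient from six pairs of values is very imprecise. Two pairings, two scales (actual values and changes) and five groups give 2 x 2 x 5 = 20 post-baseline coefficients, none based on more than 8 planned subjects. Their scatter will be mostly noise. A reader of the report could take one large coefficient as support for a dose, or small ones as evidence that lung function and symptoms are unrelated, and neither inference would be safe. Section 4.2.6 of the main SAP applies no multiplicity adjustment, so nothing in the plan tempers selection among the 20. The MAD data taken together carry considerably more information on the association than the planned display extracts.

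**Working it through.** **Inputs.** Each MAD cohort has 6 active and 2 placebo subjects (SAP 4.1). Four cohorts give 4 x 6 = 24 active subjects, 6 per dose, and 4 x 2 = 8 placebo, so 24 + 8 = 32, which reproduces the SAP's MAD total. The documents give no expected or target correlation, so values of r are assumptions: 0.5 for illustration, 0.7 as strong.

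**Formulas.**

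- 95% CI for one arm: tanh(atanh(r) ± 1.96/√(n − 3)).
- 95% CI for a partial correlation adjusting for five arms (4 indicators): the same, with standard error 1/√(N − 4 − 3).
- Critical |r| at 5% two-sided: t/√(df + t²), with df = n − 2 for one arm and N − 4 − 2 for the partial correlation.

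**Observed r = 0.5**, atanh(0.5) = 0.549.

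- n = 6: SE 1/√3 = 0.577; limits 0.549 ± 1.132, so -0.52 to 0.93.
- n = 8: SE 1/√5 = 0.447; limits 0.549 ± 0.877, so -0.32 to 0.89.
- N = 32, arm-adjusted: SE 1/√25 = 0.20; limits 0.549 ± 0.392, so 0.16 to 0.74.

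**Critical |r|.**

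- 4 df: 2.776/√(4 + 7.71) = 0.81.
- 6 df: 2.447/√(6 + 5.99) = 0.71.
- 26 df: 2.056/√(26 + 4.23) = 0.37.

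**Strong against absent.** Power was obtained from 100,000 simulated bivariate normal data sets per setting.

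| | n = 6 | n = 8 | N = 32, arm-adjusted |
|---|---|---|---|
| 95% CI at r = 0 | -0.81 to 0.81 | -0.71 to 0.71 | -0.37 to 0.37 |
| 95% CI at r = 0.7 | -0.26 to 0.96 | -0.01 to 0.94 | 0.44 to 0.85 |
| Power, true correlation 0.5 | 17% | 25% | 80% |
| Power, true correlation 0.7 | 37% | 54% | 99% |

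Within an arm the intervals at 0 and 0.7 overlap heavily. For the arm-adjusted estimate they do not overlap.

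**Chance extremes.** With no true correlation, the probability that |r| reaches 0.7 is 0.1215 at n = 6 and 0.0532 at n = 8. The chance that at least one of the five arms does so, for one pairing and scale, is 1 − (1 − 0.1215)⁴(1 − 0.0532) = 44%.

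**Sensitivity to N.** Drop-out, or use of the Per Protocol set (addendum 2.1), would lower N. For r = 0.5 the arm-adjusted interval is 0.11 to 0.76 at N = 27 and 0.01 to 0.80 at N = 20. Protocol section 5.2 allows expansion to about 96 subjects, or 12 per cohort and 48 in MAD. If 3:1 allocation is kept, the arms would be about 9 and 12. Their by-arm intervals at r = 0.5 would still be -0.25 to 0.87 and -0.10 to 0.83, against 0.24 to 0.69 for the arm-adjusted estimate.

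**The case against.** The addendum calls itself post hoc, and protocol section 13.4 treats any inferential statistics as hypothesis-generating. Section 3.3 plans no test, threshold or decision, and gives no purpose beyond assessing the relationship. Judging a descriptive display by critical values applies a standard that it does not claim. This stands as a limit on severity. It does not answer the intervals, which describe how little each coefficient says whether or not anyone tests it.

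The stronger objection is that pooling assumes one within-arm correlation. Treatment could move one measure and not the other at some doses, and the addendum itself adds an umbrella-shaped dose-response model. By-arm plots can barely check this. For two arms of 6 with true correlations 0 and 0.7, the Fisher z difference is 0.87 with SE √(1/3 + 1/3) = 0.82, giving power of about 18%. This stands, and the assumption must be declared as a limitation. It does not favour the by-arm analysis as the main result, because that analysis cannot detect such differences either. With r = 0 in one active arm, the other would need about 0.92 to differ at the 5% level, or about 0.89 for active against placebo.

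A reader might go further than the documents allow in three ways.

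- That every planned correlation is split by arm. The baseline correlation is already overall and is not criticised.
- That by-arm correlations can show nothing. An observed r of 0.9 at n = 6 has an interval of 0.33 to 0.99, which excludes zero.
- That the 10-point CFQ-R RSS bands in addendum 2.2 ("The following subgroups of CFQ-R RSS at baseline by range of 10 points will also be considered for CFQ-R RSS analyses") share the defect. Addendum 3.2 uses those bands for descriptive summaries only; its subgroup models split CFQ-R RSS at 75. Sparse descriptive cells drive no inference, so replacing them would be a matter of presentation.

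**Conclusion.** The point holds for the two post-baseline pairings and is minor. At the planned arm sizes, the by-arm correlations can rarely tell a strong association from none. Adjusting for arm over all MAD subjects narrows the interval at r = 0.5 from a width of about 1.45 (n = 6) or 1.21 (n = 8) to 0.58, and lowers the critical |r| from 0.81 or 0.71 to 0.37.

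This rests on the planned 32 subjects, approximate bivariate normality and a correlation common to the arms. The quantity estimated is a between-subject association within arms. A reader might take it as showing that the two measures move together within a subject over time, but neither the planned nor the added analysis addresses that. No safety, MTD, pharmacokinetic or prespecified efficacy result depends on it.

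**What to change.** In addendum 3.3, for each post-baseline pairing, and for actual values and changes alike, add a partial correlation across all MAD subjects adjusted for treatment group. Report it with its 95% confidence interval and the number of subjects used, as the main summary. It should be adjusted for arm, because a plain overall correlation would mix in differences between arm means. Keep the by-arm correlations, scatterplots and regression lines, labelled as descriptive. State that the estimate assumes a common within-arm, between-subject correlation, and that arms of this size can check this only weakly.

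The cost is a few lines of addendum text and four added estimates (2 pairings x 2 scales). No new data are needed and nothing planned is removed.

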### **3.4. Weight (kg) and Sweat Chloride (mmol/L)**

Analyses for Weight and Sweat Chloride will be repeated on Per Protocol Populations.
